3.1.1 Stopping criteria for dose escalation

A Safety Review Committee (see Section 6.6) will review safety and tolerability results after each dose before proceeding to the next dose.

Any safety concerns will be evaluated using the following guidance, which is based on preclinical studies with AZD3199 and knowledge from clinical experience with LABA:s:

Stopping guidance for dose escalation

• A difference of 30% in the incidence of specific criteria (as described below) between placebo and AZD3199 groups. For example, if 0 of 2 subjects on placebo and 1 of 6 subjects on active treatment are affected dose escalation would likely continue. If 0 of 2 subjects on placebo and 2 of 6 subjects on active treatment are affected stopping dose escalation would be considered.

Cardiovascular system:

- A QTcF > 500 ms (QT interval corrected for heart rate by Fredericia method) or a QTcF prolongation > 60 ms on average compared to baseline sustained for more than 30 minutes, or on 2 contiguous time points.
- A persistent (>60 min) heart rate >120 beats/min related to the study drug according to the Investigator
- A clinically significant supraventricular or ventricular tachyarrhythmia of any kind, except isolated ventricular extrasystoles according to the Investigator
- A persistent (>30 min) diastolic blood pressure <45 mm Hg related to the study drug according to the Investigator

Potassium concentrations:

A persistent (>30 min) plasma potassium concentration <2.8 mmol/L

Liver:

Increase in AST or ALT≥ 3 x upper limit of normal reference interval (ULN) or bilirubin >2 x ULN or an increase in bilirubin ≥1.5 x ULN and AST or ALT> 2 x ULN.

Any other clinically relevant changes and significant changes in the safety parameters (e.g. ECG parameters, blood pressure, pulse, spirometry, body temperature, laboratory assessments and AEs) making the continuation of dosing unjustified.

Dose escalation will be stopped if the mean total plasma AUC or C_{max} of AZD3199 is higher than 111 nmol/L*h or 63 nmol/L, respectively. (Section 3.2.1)

GEL Version ID: RITA.000-199-834.2.0 Approved by 23(95)

Approved

Date Printed:

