3.2 Rationale and risk/benefit assessment

3.2.1 Rationale for study design, doses and control groups

This is the first clinical study with AZD3199. Part A of this study is designed to assess the safety, tolerability and pharmacokinetic (PK) profile of inhaled AZD3199 when administered to healthy male volunteers as a single dose. Part A will help the selection of appropriate doses of AZD3199 for Part B.

A double-blind design regarding treatment (active or placebo) within each dose group was selected in order to avoid bias from the subjects' knowledge of treatment. The placebo control will provide a reference to aid interpretation of safety and tolerability data. One single dose will be administered to each subject to avoid repeated exposure of the study drug to one individual. Food/water intake will be standardised/restricted to keep the conditions similar between subjects and to minimize variability on the ECG monitoring and potassium concentrations levels.

Subjects in *the two last* dose groups will be resident at the clinic an extra day, to perform an ECG dummy day before dosing starts. This will be done to obtain individual correction factors to be used in the calculations of QTc for each subject after administration of AZD3199.

Healthy non-nicotine using men aged 18-45 years will be included in order to minimize the effects of concomitant disease states or medications on study measurements. The study is restricted to male subjects, since sufficient reproduction toxicology data in female animals is not yet available. The inclusion and exclusion criteria for Part A are chosen in order to select subjects who are known to be free from any significant illness.

The beta adrenergic receptor is a well known target for pharmacological intervention and inhaled LABAs have been in clinical use for more than 10 years, thus it would not be categorized as high risk as defined in the EMEA guideline for First Time in Man studies. The starting dose of AZD3199 will thus consider although not be strictly conditioned by the Minimal Anticipated Biological Effect level (MABEL) concept in this study. When deciding the starting dose in this study the FDA guidance "Estimating the maximum safe starting dose in initial clinical trials for therapeutics in adult healthy volunteers 2005" and the predicted pharmacologically active human dose have been taken into consideration. This is further described in the Investigator's Brochure (IB).

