A first lung deposited dose of 1/10 of the dose anticipated to be minimally clinically relevant, is aimed for in the first time into man study giving a rounded off value of 2 μ g/60 kg. The maximum lung deposited dose will be <200 μ g/kg, ie, <12000 μ g/60 kg (limits set by NOAEL in the rat, and gradually increasing systemically mediated class effects in the dog above NOAEL) or the dose giving a mean C_{max} of >63.0 nmol/L or a mean AUC of

Approved by

>111 nmol/L*h (total mean plasma exposures at NOAEL in the rat). The incremental dosing will consider observed local and systemic effects and the expected clinically relevant level. Markers of systemic pharmacological activity in the AZD3199 SAD study are a decrease in plasma potassium, tremor and an increase in heart rate. If these are noted the dose escalation pace will be slowed down (Section 3.4.2.1).

Adrenaline is the non-selective endogenous prototype for synthetic non-selective β - or selective β_2 - adrenoreceptor stimulants. Tremor is likely to be mediated via stimulation of the β_2 -adrenoceptor on the plasma membrane of skeletal muscles. Positive chronotropic and inotropic effect on the heart is primarily mediated via stimulation of the β_1 -adrenoceptor, but selective β_2 -agonists still have such cardiovascular effects via the less frequently abundant β_2 -adrenoreceptor. Furthermore, stimulation of β_2 -adrenoceptors can increase the cellular uptake of potassium, induce peripheral vasodilatation, and have a calorigenic effect. Thus, systemically mediated dose-dependent effects of inhaled AZD3199 could be increased incidences of reported tremor or tachycardia/palpitations, increased systolic blood pressure, decreased extracellular concentration of potassium, decreased diastolic blood pressure, or increased concentration of glucose and lactate (the latter because the supply of oxygen to muscles and capacity for glycogenesis are limited). These well known potential side-effects upon β -adrenoreceptor stimulation will be monitored.

The number of samples and time points for measurements may be adjusted if justified from the emerging PK and safety profile of AZD3199.

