3.4.2.1 Adjustment of dose levels

The incremental dosing will consider observed local and systemic effects and the expected clinically relevant level. The planned dose levels may be changed, postponed or repeated during the course of the study depending on safety, pharmacodynamic and pharmacokinetic results obtained. The SRC will make a safety evaluation between each dose level and change the dose escalation, if necessary, see Section 6.6. The SRC makes all decisions regarding modification of dose levels.

If, on a certain dose level a systemic pharmacological effect of AZD3199 is seen, ie,

- a mean decrease of potassium C_{min} of more than 0.25 mmol/L compared with placebo related to the study drug

or

.

a mean increase of maximum resting pulse of more than 15 beats/min compared with placebo related to the study drug

the suggested dose escalation factor for the future doses will be re-evaluated and lowered to a maximum of 3.

After each Safety Committee evaluation personnel dispensing investigational product at the hospital pharmacy and the personnel at IPS, AstraZeneca R&D will be informed about the decision for the next dose escalation and IPS will issue a corresponding dosing schedule.

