6.6 Safety Review committee

Safety and tolerability will be evaluated by a Safety Review Committee (SRC).

The study will be blinded at the dosing occasion. The SRC will receive blinded data prior to the meeting, but will have access to unblinded data at the SRC meeting in between each dose cohort.

The SRC will consist of medical expertise. The chairman of the committee will be the Clinical Study Team Physician. The other experts will be the Principal Investigator, the Medical Science Director and the Global Drug Safety Physician. Other relevant expertise (eg, medical, statistic, pharmacokinetic, drug safety) will be consulted if deemed necessary. The members of the committee will review interim study data and decide upon the progression of dosing from one dose level of AZD3199 to the next. Safety and tolerability data (ECG parameters, blood pressure, pulse, body temperature, lung function, safety laboratory variables, and adverse events) and potassium and lactate concentrations from the

first 24 hours after dose and available PK results will be evaluated prior to progression to the next dose level. Data obtained more than 24 hours after the dosing (adverse event reports and laboratory safety variables) must be reviewed by the Investigator and communicated with the SRC. The SRC will decide whether to:

- continue to next planned dose
- escalate or de-escalate the next dose level
- repeat a previous dose level
- postpone the next dose level
- terminate the study

PLEASE CHECK ITS VALIDITY BEFORE USE

AN ELECTRONIC DOCUMENT.

A PRINTED COPY OF

ы И

THIS

The decision of the SRC will have to be taken in consensus. The decisions and decision-making will be noted by the chairman and a written recommendation will be provided to the study site and IPS AstraZeneca R&D, prior to the next scheduled dose group. The SRC and/or the principal investigator will have the full authority to terminate the study at any time during the course of the study.

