12. PART B - STUDY PLAN AND PROCEDURES

12.1 Overall study design

This Clinical Study Protocol has been subjected to a peer review according to AstraZeneca standard procedures.

Part B will be a single-blind, non-randomised, placebo-controlled, crossover study with single ascending dose levels of inhaled AZD3199 investigating the efficacy, tolerability, safety and PK in patients with asthma aged 18-50 years. This part of the study will be carried out at 1 or more centres.

Part B will comprise a maximum of 4 dose levels and will employ 2 cohorts of 8 patients. Each cohort will receive one placebo treatment and 2 different doses. No doses will exceed the highest doses given to the healthy subjects.

The administration of AZD3199 in Part B will start when clinical and/or laboratory data from the healthy volunteers in Part A indicate systemic effects, or if no systemic effects are seen, when 5 dose levels have been administered in Part A. Markers of systemic pharmacological activity are primarily a decrease in plasma potassium and an increase in heart rate.

The following criteria will be used:

• a mean decrease of potassium C_{min} of more than 0.25 mmol/L compared with placebo related to the study drug

or

a mean increase of maximum resting pulse of more than 15 beats/min compared with placebo related to the study drug

Dose escalation will only proceed after a safety review of data generated at the previous dose level(s). At the end of each dose level, an interim data assessment will be made by a Safety Review Committee (SRC) to determine the next dose. This evaluation will be based both on efficacy (up to 26 hours), safety and tolerability (data from at least the first 12 hours after dose) and available PK results. The SRC will decide which dose to give next, see Section 15.6.

The study will be single-blind, ie, open to the study site personnel and SRC, but the patients will not be informed about the dosing order.

The patients will be resident at the clinic from the evening before dosing until 48 hours (h) following each dose. The length of the residence period at the clinic, assessments and the follow up period may be adjusted if felt necessary.

Patients will be fasting from 22:00 the day before dosing until 4 hours post dose. Standardised lunch and dinner avoiding potassium rich food will be served at 4 and 8-10 hours after drug administration.

59(95)

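### Applied to a cohort's own two placebo subjects, the Part A stopping guidance rises from 2 of 6 to 5 of 6 active subjects as soon as one placebo subject is affected

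*Protocol*

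**What the plan says.** In Part A each dose level has six active and two placebo subjects (Section 3.1). Section 3.1.1 gives the SRC guidance on stopping escalation. Its numeric incidence element is "A difference of 30% in the incidence of specific criteria (as described below) between placebo and AZD3199 groups". Two illustrations follow, both with no placebo subject affected. With one of six active subjects affected, escalation is expected to go on. The other reads: "If 0 of 2 subjects on placebo and 2 of 6 subjects on active treatment are affected stopping dose escalation would be considered". There is no illustration with a placebo event, and nothing says whether placebo subjects from earlier cohorts count.

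Six specific criteria are listed. Heart rate and diastolic pressure count only if the investigator relates them to study drug. QTcF, tachyarrhythmia, potassium and liver criteria carry no such condition. The section also has a catch-all for other clinically relevant changes, and a separate stop on mean AUC or Cmax. Neither depends on placebo.

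Under Section 6.6 the SRC "will have access to unblinded data at the SRC meeting in between each dose cohort". Section 6.3.4 pools placebo subjects across dose levels for safety and pharmacodynamic comparisons, but it describes the statistical analysis and Section 3.1.1 does not refer to it.

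Section 3.4.2.1 sets two further triggers. One is a mean fall in minimum potassium "of more than 0.25 mmol/L compared with placebo related to the study drug". The other, repeated in Section 12.1, is "a mean increase of maximum resting pulse of more than 15 beats/min compared with placebo related to the study drug". If either is met, "the suggested dose escalation factor for the future doses will be re-evaluated and lowered to a maximum of 3". Neither section says which placebo subjects are meant.

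**The concern.** A proportion out of two can only be 0, 50% or 100%. A fixed 30-point difference against it therefore behaves very differently once a single placebo subject is affected. Four of the six criteria can be met by chance in a placebo subject, for example by a transaminase rise unrelated to treatment. If that happens, four active subjects meeting the same criterion fall below the stated threshold.

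This is the only incidence threshold in the escalation guidance of a first-in-human study. A committee following it literally would not be prompted in a cohort where most active subjects were affected.

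**Working it through.** **Inputs.** Six active and two placebo subjects per level (Section 3.1); a 30-point threshold and two illustrations (Section 3.1.1). The protocol gives no event rates, so the rates below are assumptions. All chances are per criterion and per cohort.

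**The plan's own examples.** 1/6 − 0/2 = 16.7 points, below 30. 2/6 − 0/2 = 33.3 points, at or above 30. Both reproduce, with the threshold read as an absolute difference (a relative one is undefined at 0 of 2).

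**Smallest active count x with x/6 − a/2 ≥ 0.30, and chance of reaching it by true active rate.**

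| Placebo affected (a of 2) | Active needed | Check | Rate 1/3 | Rate 1/2 | Rate 2/3 |
|---|---|---|---|---|---|
| 0 | 2 of 6 | 2/6 − 0 = 0.333 | 0.65 | 0.89 | 0.98 |
| 1 | 5 of 6 | 4/6 − 1/2 = 0.167; 5/6 − 1/2 = 0.333 | 0.02 | 0.11 | 0.35 |
| 2 | none | 6/6 − 2/2 = 0 | 0 | 0 | 0 |

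**How often this arises.** With placebo rate p, the chance that at least one of two is affected is 1 − (1 − p)²: 2.0% at p = 1% and 9.8% at p = 5%.

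**Average chance of a flag** = (1 − p)² × P(at least 2 of 6) + 2p(1 − p) × P(at least 5 of 6).

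- Active rate 30%: P(at least 2) = 0.580 and P(at least 5) = 0.011. At p = 1%: 0.9801 × 0.580 + 0.0198 × 0.011 = 0.569. At p = 5%: 0.9025 × 0.580 + 0.095 × 0.011 = 0.524. The losses are 1.1 and 5.5 points.
- Active rate 50%: P(at least 2) = 0.891 and P(at least 5) = 0.109. At p = 1%: 0.875. At p = 5%: 0.814. The losses are 1.6 and 7.7 points.

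**If placebo were pooled to date, as in Section 6.3.4.** With one placebo subject affected in total, the count needed is:

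- cohort 2 (4 placebo): 4 of 6, since 3/6 − 1/4 = 0.25 and 4/6 − 1/4 = 0.417;
- cohort 3 (6 placebo): 3 of 6, since 3/6 − 1/6 = 0.333;
- cohorts 4 to 8: also 3 of 6. Even with 16 placebo subjects, 2/6 − 1/16 = 0.271 falls short.

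**Extra prompts from a rule of 2 or more of 6 active.** With the same true rate in both arms, the chance of a prompt goes from 3.0% to 3.3% per cohort at a 5% rate, and stays at 0.1% at a 1% rate.

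**Potassium trigger, as context for the clarification.** The protocol gives no SD; assume 0.25 mmol/L (range 0.20 to 0.30) and SE = SD × √(1/6 + 1/n). With no true effect, the 0.25 mmol/L difference is exceeded in 11% (6% to 15%) of levels with n = 2 placebo subjects. With the 8 available at Dose 4 it is 3% (1% to 6%). These are chances of meeting the number; the criterion also requires relation to study drug.

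**The case against.** A reader might infer that the guidance stops working after one placebo event, or that escalation is then left without a brake. The documents do not support this. With one placebo subject affected the threshold can still be reached at 5 or 6 of 6. The text is worded as guidance, the catch-all allows stopping whatever happens on placebo, and the SRC reviews unblinded safety data before every escalation.

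The two-subject denominator appears only in illustrations. If the SRC pooled placebo as Section 6.3.4 does for safety data, the case of 4 of 6 going unflagged with one placebo event would be confined to the first cohort. This stands as a limit on the point, but Section 3.1.1 does not say that pooling applies, and both of its illustrations use two.

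A placebo-relative criterion is also a legitimate choice. Section 3.2.1 says "The placebo control will provide a reference to aid interpretation of safety and tolerability data", and an affected placebo subject does weaken the case that the drug is the cause. But 1 of 2 says little about the placebo rate: the exact 95% interval runs from 1 − √0.975 = 1.3% to √0.975 = 98.7%. That is a reason to show the placebo events to the SRC, not to let one of them raise the threshold to 5 of 6.

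Finally, placebo events on these criteria should be uncommon in screened healthy men; Section 3.3.3 already excludes QTcF above 450 ms. This stands, and it keeps the average loss small.

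On the potassium and pulse triggers, a reader might infer that the comparison is undefined and the triggers therefore unreliable. That goes too far. Section 6.3.4 states a pooled placebo set for pharmacodynamic comparisons, and what is missing is a cross-reference. Planned steps above Dose 5 are already below the cap of 3 (1500/640 = 2.3, 3000/1500 = 2, 4500/3000 = 1.5), so on the planned doses the cap affects only the steps up to Dose 5.

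**Conclusion.** The point holds in limited form. Applied to the concurrent two placebo subjects, as the protocol illustrates it, the 30% guidance needs 2 of 6 active with no placebo event, 5 of 6 with one, and cannot be met with two. The counts are exact. The average loss of about 1 to 8 points rests on assumed placebo rates of 1% to 5% and active rates of 30% to 50%, and would be smaller after the first cohort if the SRC pooled placebo. This is a cheap improvement worth considering, not a failure of the safety plan.

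The potassium and pulse wording does not stand as a finding on its own; its figures depend on an SD that the protocol does not give.

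**What to change.** Keep the 30% guidance and add to Section 3.1.1: *In addition, if 2 or more of the 6 active subjects in a cohort meet a criterion, the SRC will consider stopping dose escalation. Placebo events will be shown as context, both for the cohort and pooled over all placebo subjects to date.* The count of 2 of 6 is the protocol's own, the placebo comparison stays in view, and the decision stays with the SRC.

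As a clarification only, let Sections 3.4.2.1 and 12.1 refer to the pooled placebo set of Section 6.3.4 for the potassium and pulse differences. Show the concurrent two separately, because Section 3.1 allows sampling times to change during the study and minima and maxima depend on the sampling grid.

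The cost is a few sentences of wording, with no added subjects, visits or unblinding. The downside is an occasional extra SRC discussion, including some where placebo subjects are equally affected.

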3. PART A - STUDY PLAN AND PROCEDURES

3.1 Overall study design

This Clinical Study Protocol has been subjected to a peer review according to AstraZeneca standard procedures.

Part A will be a double-blind, randomised, placebo-controlled study with single ascending dose levels of inhaled AZD3199 to investigate the tolerability, safety and PK in healthy men aged 18-45 years. This part of the study will be carried out at 1 or more centres.

Part A will comprise a maximum of 8 dose levels and each dose escalation will employ a new cohort of subjects. At each dose level, 8 subjects will be dosed of which 6 will receive AZD3199 and 2 will receive placebo. In total 64 subjects will be randomised.

Dose escalation will only proceed after a safety review of data generated at the previous dose level(s). The first lung deposited dose to man of AZD3199 will be $2\mu g$ (1/10 of the minimum dose anticipated to be clinically relevant). At the end of each dose level, an interim data assessment will be made by a Safety Review Committee (SRC) to determine the next dose. Adjustment of doses are guided by criteria for dose escalation pace, see Section 3.4.2.1 and stopping criteria, see Section 3.1.1. Dose escalation may continue until the defined maximal exposure (AUC or C_{max}) of AZD3199 is reached, or predicted to be reached, unless the maximum tolerated dose has been reached before. The SRC will decide which dose to give next, see Section 6.6.

The subjects will be resident at the clinic from the evening before dosing until 48 hours (h) following each dose. The length of the residence period at the clinic, assessments and the follow up period may be adjusted if justified. In addition, the two last dose groups will be resident at the clinic for 36 h before dosing, to allow for a dummy day with ECG measurements.

Subjects will be fasting from 22:00 the evening before dosing until 4 hours post dose. Standardised lunch and dinner avoiding potassium rich food will be served at 4 and 8-10 hours after drug administration.

Part A of this study comprises 4 visits (see Figure 1 and Table 1); 2 screening visits, a treatment visit and a follow-up visit.

Visits 1 and 2 are screening visits. At Visit 1 informed consent will be obtained before any study related procedures are undertaken. Visits 1 and 2 will be performed within 30 days prior to randomisation and intake of study drug.

19(95)

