In this study, beside the final analysis, the ECG Centre will deliver, at agreed upon dates, a safety evaluation of the digital ECG data to be submitted to the Safety Review Committee for evaluation. Upon completion of ECG recordings for each dose group, the digital files are transferred at specified time points from the CS 200 to the local server (LEFTS) at CPU Astra Zeneca R&D Lund. Accredited users can correct metadata on the LEFTS, using the GAME File Viewer and also monitors success of transfer. A printout from GAME File Viewer must be checked, signed and stored at the CPU for monitoring purposes. From LEFTS, the digital ECG files are transferred with checksum-protection to the central server (CEFTS). Transfer logs are kept and signed by the local GAME administrator.

From the CEFTS, the source ECGs will be imported into the EClysis[©]system. From the continuous ECG recording, 10-second ECGs are retrieved twice per minute and analysed by the dedicated ECG Scientific Advisor at the ECG Centre, who will perform a preliminary analysis in lead V2 with main focus on QT changes, wave morphology changes and dysrhythmia. The ECG Centre Cardiologist will perform the ECG evaluation and interpretation of findings and will provide a Safety report.

On study completion, the ECG Scientific Advisor will ensure that all protocol-defined ECGs have been imported into EClysis[©] databases and will then perform the final analysis with any required corrections of the ECG annotations provided by EClysis[©]. An external cardiologist will conduct the final review and adjustments before locking the EClysis[©] database into a read only state containing all results, with all actions logged into the audit trail and Event log in a user- and time- attributable manner. The results from the locked database will then be exported in secure, checksum-protected files, which are accessible on the CEFTS to the accredited Programmer for conversion into SAS files for statistical analysis.

In this study the following data from lead V2 will be analysed and reported as primary: RR, PQ (PR), QRS, QTtang. Lead V5 will be analysed, for all visits, as backup for the individual where analysis in lead V2 is not deemed possible for pre-dose or significant parts of whole visit.

Approved

A PRINTED COPY OF AN ELECTRONIC DOCUMENT. PLEASE CHECK ITS VALIDITY BEFORE USE

5 H

THIS

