13.4.2 Electrocardiographic measurements

13.4.2.1 Resting 12-lead ECG

PLEASE CHECK ITS VALIDITY BEFORE USE

ELECTRONIC DOCUMENT.

AN

ЪО

PRINTED COPY

IS A

THIS

12-lead ECG recordings will be obtained after 10 minutes rest in the supine position, at the time points indicated in the time plans (see Table 6 and Table 7). The patient must have the same position (max 30 degrees) during all ECG registrations. A print out at paper speed 50 mm/sec will be used. Heart rate, QT and an overall evaluation, normal / abnormal (specified) will be recorded in the CRF for ECGs collected predose, and 30 minutes to 12 h post dosing. For ECGs collected at Visits 2 and 6 and the 48 h post dose ECGs at Visits 3-5 only an overall evaluation, normal/abnormal (specified) will be recorded.

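### Part A stopping guidance (Section 3.1.1): the 30% incidence rule and its 1-of-6 example lean towards escalation even after a single ventricular tachyarrhythmia or confirmed QTcF above 500 ms

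*Protocol*

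**What the plan says.** Section 3.1.1 (Part A) opens its stopping guidance with a single threshold: "A difference of 30% in the incidence of specific criteria (as described below) between placebo and AZD3199 groups". Two worked cases follow. In the first, "if 0 of 2 subjects on placebo and 1 of 6 subjects on active treatment are affected dose escalation would likely continue". In the second, with 2 of 6 active and 0 of 2 placebo subjects affected, stopping is to be considered.

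The criteria under that threshold are cardiovascular, potassium and liver items. They include QTcF above 500 ms and this one: "A clinically significant supraventricular or ventricular tachyarrhythmia of any kind, except isolated ventricular extrasystoles according to the Investigator". None has a separate single-event rule. After them come a general item for any other clinically relevant safety change that makes continued dosing unjustified, and a limit on mean AUC and Cmax.

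Section 3.4.2.1 has a slow-down rule. If a systemic effect is seen, "the suggested dose escalation factor for the future doses will be re-evaluated and lowered to a maximum of 3". The triggers are a mean fall in minimum potassium of more than 0.25 mmol/L, or a mean rise in maximum resting pulse of more than 15 beats/min, each against placebo.

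Section 6.6 requires an SRC decision before each next dose level. The SRC "will have access to unblinded data at the SRC meeting in between each dose cohort" and must decide by consensus.

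**The concern.** The listed criteria differ greatly in gravity. A rule that compares incidences is reasonable for a passing potassium or blood pressure finding, where one subject in six may well be noise. A ventricular tachyarrhythmia or a confirmed QTcF above 500 ms in a healthy man is different. Section 3.3.3 excludes anyone with QTcF above 450 ms, so a value above 500 ms lies more than 50 ms above any eligible screening value. Section 3.2.2 names QTc prolongation and heart rate increase in the dog as potentially relevant to humans.

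The subjects are healthy volunteers without individual benefit, in the first study of the drug in man. The question for the SRC after one such event is whether the drug caused it. The written guidance poses a different question, whether the incidence difference reaches 30%, and for one event in six it suggests going on to the next dose.

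**Working it through.** **Inputs.** Six active and two placebo subjects per dose level (Section 3.1). Threshold 30% (Section 3.1.1). Planned lung deposited doses of 2, 10, 40, 160, 640, 1500, 3000 and 4500 µg (Section 3.4.2, Table 4). The protocol gives no event rate, so the rates in step 3 are assumptions.

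**1. The plan's own example.**
- 1/6 − 0/2 = 16.7%, below 30%: continue.
- 2/6 − 0/2 = 33.3%, above 30%: consider stopping.

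Both cases agree with the stated threshold. With no placebo subject affected, the trigger is therefore two of six active subjects, and a single event of any listed kind does not meet it.

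**2. How much one event in six tells.** The exact (Clopper-Pearson) 95% interval for 1/6 runs from 0.4% to 64.1%. One event does not rule out a true rate well above 30%.

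**3. How often the continue case arises.** For six active subjects with true rate p, P(exactly one) = 6 × p × (1 − p)^5. At p = 0.30 this is 6 × 0.30 × 0.1681 = 0.303. P(none) = 0.7^6 = 0.118, and P(two or more) = 0.580.

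| Assumed true rate | None | Exactly one | Two or more |
|---|---|---|---|
| 5% | 73.5% | 23.2% | 3.3% |
| 10% | 53.1% | 35.4% | 11.4% |
| 20% | 26.2% | 39.3% | 34.5% |
| 30% | 11.8% | 30.3% | 58.0% |

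Only the exactly-one column bears on this point, because a single-event rule changes nothing in cohorts with no event. At rates up to 20%, an affected cohort is more likely to show one case than several, so the 1-of-6 example is then the guidance that applies. That holds for any uncommon event in six subjects. It matters here because of how grave these two events are.

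**4. Size of the next step.** Ratios of successive planned doses:
- 10/2 = 5
- 40/10 = 4
- 160/40 = 4
- 640/160 = 4
- 1500/640 = 2.34
- 3000/1500 = 2
- 4500/3000 = 1.5

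A cap of 3 would bind only after levels 1 to 4. Its triggers are group means of potassium and pulse, so one arrhythmia or one QTcF event does not set it off.

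**5. Comparison with Part B.** Section 12.1.1 lists the same QTcF and tachyarrhythmia criteria without an incidence threshold, and Section 12.3.5.1 makes such events grounds for discontinuing the individual patient. Part B re-exposes the same patient, so the purpose differs. It does show that these criteria can work without the 30% filter.

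**The case against.** The strongest reply is that Section 3.1.1 is guidance and other provisions already protect subjects. The examples say what would likely happen or be considered, and they illustrate arithmetic without ordering anything. The SRC sees unblinded data and must agree by consensus, so one dissenting member blocks escalation. It can change, postpone or repeat a dose level. The SRC and/or the principal investigator may terminate the study at any time (Section 6.6). Telemetry is displayed for at least 48 hours and watched by the investigator or a delegate (Section 4.4.2.2). The general item in 3.1.1 has no 30% threshold and names ECG parameters and adverse events. The 4- to 5-fold steps end at 640 µg, and levels 1 and 2 lie below the 35 µg estimated in Section 12.2.1 to be the therapeutic lung dose.

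Most of this stands, and it sets the size of the point. A reader might infer that the protocol obliges escalation after a grave event, or lets it go ahead unreviewed. The text does not support that.

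Two parts of the reply are weaker. The general item speaks of any other changes, so it does not clearly override the threshold for criteria already listed. The discretionary powers also leave untouched the direction in which the written guidance points when the committee turns to it.

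A reader might also infer that the lack of a stated hold for undosed subjects of the same cohort is a defect in itself. It matters only if dosing within a cohort is staggered. The protocol does not say so, and the separate administration instructions cited in Section 3.4.2.3 are not shown. Nor does the text support a claim that QT results come too late for the escalation decision: the ECG Centre's safety evaluation goes to the SRC (Section 5.7.4).

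**Conclusion.** The point holds as a weakness in the guidance and not as a loss of control. Section 3.1.1 applies one 30% difference to events of very different gravity, and its example leans towards continuing after a single ventricular tachyarrhythmia or a single confirmed QTcF above 500 ms. The slow-down rule does not correct that lean, and the next planned step is 4- to 5-fold after levels 1 to 4.

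If the true rate on active drug were 30%, 30% of cohorts would fall into the continue case. At assumed rates of 5%, 10% and 20% the figures are 23%, 35% and 39%. No reduction in the number of subjects exposed is claimed, because the timing of dosing within a cohort is not stated. The change is an inexpensive improvement and not a condition for the study to proceed.

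**What to change.** Add to Section 3.1.1:

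*The 30% difference and its example do not apply to a clinically significant ventricular tachyarrhythmia, or to a QTcF above 500 ms confirmed as lasting more than 30 minutes or as present at two consecutive time points. After one such event in a subject on AZD3199, the dose is not escalated unless the SRC, at its unblinded meeting, documents why the event is not considered related to the study drug.*

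The confirmation wording keeps one stray reading from holding up the study. In the present text it is unclear whether the duration qualifier applies to the 500 ms limit as well as to the 60 ms prolongation.

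Only if dosing within a cohort is staggered, add a further sentence: after such an event, the investigator pauses further dosing in that cohort until the SRC chairman has reviewed it. Section 3.4.4.2 already gives the chairman the individual codes, so the site need not be unblinded.

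The cost is two sentences, or three with staggered dosing, using the existing committee, criteria and codes. The downside is an occasional delayed escalation for an event that proves unrelated or, with staggered dosing, an occasional pause for one that proves to be on placebo. The SRC stays free to escalate once it has recorded its reason.
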